14. BIOSTATISTICS

This is a pilot interventional study to evaluate the feasibility of high dose rate (HDR) brachytherapy using image-guided navigational techniques as salvage therapy for previously treated lesions of the spine. The primary outcome that we wish to assess is the reproducibility of the treatment plan parameters; secondary outcomes include toxicity, relief of pain, and local disease progression.

In terms of technical feasibility, a patient is regarded as being successfully treated if the target D90 is $\geq 80\%$ AND the cord/cauda max dose is 8 Gy. To this end we will enroll 20 patients and declare the procedure feasible if at least 15 patients can be successfully treated. For this decision rule we have the following probability table:

True feasibility rate	55%	60%	65%	70%	75%	80%	85%	90%
Probability of declaring feasible	0.055	0.126	0.245	0.416	0.617	0.804	0.933	0.989

We believe this procedure will be quite safe for patients; a previous study from Japan [Seichi 1999] showed serious toxicity rates of approximately 3%, and we anticipate ours will be even lower. Among the 20 patients we expect to see less than 2 adverse events. In the event that a second serious adverse event (\geq Grade 3, or as otherwise defined above in Section 11.0) occurs, this protocol will be immediately halted and the investigator will carefully examine the cases with the assistance of the co-principal investigator and at least one investigator from both Medical Physics and Radiology and review the protocol (to be either terminated or modified in order to proceed further). Self-reported pain scores will be recorded and descriptive statistics regarding time to, degree of, and duration of relief from pain (if any) will be summarized numerically and/or graphically. In-field progression-free probability will be estimated using Kaplan-Meier estimation.

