2.0 OBJECTIVES AND SCIENTIFIC AIMS

The objective of this study is to validate methods of delivering adequate conformal dose to spinal and pelvic targets with HDR catheters using image-guided navigational techniques.

The Specific Aims of this study are to:

1. Verify feasibility of HDR treatment of spinal and/or pelvic lesions using catheters placed under image-guided navigational techniques, to provide improved dosimetric coverage of lesions such that
 - a. Gross Target Volume (GTV) D90 \geq 80%
 - b. Cord/Cauda max dose (Cord/Cauda Dmax) of < 8 Gy

Secondary objectives:

1. Demonstrate safety of HDR brachytherapy for previously irradiated lesions of the spine and/or pelvis, defined as an acceptable level of severe toxicity (both acute and late effects) in the setting of HDR brachytherapy treatment. Severe toxicity will be defined as \geq grade 3 NCI CTCAE v 4.0 toxicity that is at least possibly related to treatment (see Appendix 2).
2. Assess patient pain scores referable to the treatment site using the standardized 11-point pain scale.
3. Assess patients for duration of in-field progression-free survival at the treatment site.

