3.3 Published Outcomes with HDR brachytherapy for spine lesions

HDR brachytherapy for spine lesions is a novel technique developed at Memorial Sloan-Kettering Cancer Center; previous techniques have used either electron cone applicators requiring an invasive open procedure with poor conformality (Seichi 1999); the INTRABEAM electron applicator (XRS 4, Carl Zeiss Surgical Oberkochen, Germany) which delivers a non-conformal dose via a percutaneous technique (Schnieder 2011), and injection of samarium-153 during kyphoplasty, again with limited conformality (Cardoso 2009).

We have presented on our own limited experience in HDR brachytherapy for palliation of previously treated lesions in the spine at the World Congress of Brachytherapy in May of 2012. [Yamada 2012] In our experience, 5 patients were identified with progressive disease at multiply irradiated sites in the spine; 2 patients subsequently received HDR brachytherapy using catheters placed intraoperatively in the vertebral bodies during surgery and 3 patients have been treated using percutaneously implanted catheters with the assistance of interventional radiology. All treatments were performed using a two-stage interstitial catheter system (Mick Radionuclear, Mt. Vernon NY) and GammaMed Plus HDR afterloaders (Varian Medical Systems). In all cases treatment was successfully delivered with no brachytherapy-related complications. At a median followup of 4.8 months, there has been no local progression of disease. Median dose delivered was 14 Gy (range 12-18 Gy) with a median GTV V90 of 77% (range 40-89%) and median GTV D90 of 75% (range 31-94%). (Appendix 3, figures 1 and 2 show a representative plan). In all cases the spinal cord/cauda maximum dose constraints were met. No significant difference was noted between the intraoperative or percutaneous approach. 3 patients (60.0%) had pain relief 1-4 weeks following treatment. It was noted that patients with lower D90 coverage had suboptimal HDR brachytherapy catheter placement, and coverage improved rapidly with experience.

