 - d. Final setup picture with catheters in place will be taken and placed in the patient's treatment chart.

Treatment planning: as currently performed without new devices or techniques.

1. Intraoperative CT scans will be transferred to our treatment planning system (Brachyvision) with the assistance of Brachytherapy Physics:
 - a. Catheter positions will be digitized for planning by Brachytherapy Physics.
 - b. The vertebral body/paraspinal tissue and/or pelvic lesion will be contoured to provide the gross target volume (GTV), as well as a clinical target volume (CTV) to encompass potential microscopic disease; in some cases the GTV = CTV, at the discretion of the planning radiation oncologist.
 - c. Associated critical structures that have received significant prior radiation dose such as esophagus, bowel, kidneys, and rectum will be contoured and appropriate dose constraints will be applied as per standard practice. In all cases the spinal canal, cord and/or cauda will be contoured.
2. The final treatment plan will be generated by Brachytherapy physics based on the post-placement images utilizing computer optimized three dimensional treatment planning.

MEMORIAL SLOAN-KETTERING CANCER CENTER IRB PROTOCOL #: 12-260 A(4)

- a. The following dose constraints will be used for treatment planning:
 - i. Prescribed dose is 14 Gy to the periphery of the GTV.
 - ii. GTV coverage by the prescription dose will at least be 80% (D90 \geq 80%).
 - iii. Maximum cord dose (cord Dmax) will be 8 Gy.
 - iv. For lesions in close proximity (<5cm) to visceral organs, the relevant constraints will be applied:
 1. Esophagus max dose (esophagus Dmax) will be 9 Gy.
 2. Kidney max dose (kidney Dmax) will be 11 Gy.
 3. Bowel/Rectum max dose (bowel/rectum Dmax) will be a BED Gy equivalent of 85 Gy in 2 Gy fractions (accounting for all prior treatment).
3. Plan will be reviewed and approved by the radiation oncologist.
 - i. If the target dose of 14 Gy to the GTV cannot be met without exceeding dose constraints to the cord and other organs-at-risk, the highest achievable dose will be delivered that does not exceed dose constraints to organs at risk (spinal cord/cauda, esophagus, kidney, or bowel).
4. The treatment plan will undergo quality assurance procedures as per routine.

Treatment delivery and completion of care: as currently performed without new devices or techniques.

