10.0 EVALUATION DURING TREATMENT/INTERVENTION

Dosimetric planning will be performed on pre-implantation planning CT and then merged with post-implant CT images obtained following catheter placement. Specific dosimetric parameters will include GTV V90, V100, V150, V200, D90, and cord/cauda dose volume histograms. Treatment complications will be monitored in terms of radiation related toxicity during post-procedure recovery and during followup visits; all patients treated on this protocol will be evaluated regardless of whether dosimetric goals were met.

Regular follow up visits will be scheduled at 2 months (+/- 2 weeks) and then at 3 month (+/- 2 weeks) intervals until approximately 11 months of follow up. During these follow up visits, standard evaluations currently performed on all spine and/or pelvic radiation therapy patients (physical examination and imaging) will be performed. Thus, no activities that are not currently billed will be necessary. Follow up after 1 year will be performed as per standard clinical practice with no further protocol obligations.

If after the 2 month follow up a patient is not available to come in for a follow up visit, a telephone follow up by a clinical investigator will be allowed for up to two of the remaining follow up visits. If a phone call follow up is used, the physical exam will be foregone. Outside imaging studies are also allowed but must be reviewed at MSKCC.

	Screening	Treatment	Follow up (2 months post-treatment, then every 3 months until approximately 11 months of follow up)
Review of pathology	X		
Review of prior treatment	X		
Medical history	X		
Physical Exam, including neurological assessment and ambulation assessment	X		X
KPS	X		
CBC	X		
Comprehensive Serum Chemistry	X		
INR/PTT	X		
CT spine or pelvis ¹ (without contrast)	X ²	X	X ³
MRI spine or pelvis ¹ (unless contraindicated)	X		X
Pre-operative workup	X		
AE assessment	Baseline comorbidities		X
Pain assessment	X		X
Review of Commeds	X		
Pregnancy test	X		
HDR		X	

1 Imaging location will be dependent on the lesion site of interest

2 CT scan in prone position is required unless a supine CT has already been performed within 30 days of planned treatment

3 Optional if MRI is performed

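### Do the conflicting V90 and D90 figures in the background leave the reference dose for the primary D90 ≥ 80% criterion unsettled?

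*Combined protocol and SAP*

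**What the plan says.** Section 14 defines the primary outcome patient by patient: "a patient is regarded as being successfully treated if the target D90 is" at least 80% and the cord/cauda maximum dose criterion of 8 Gy is met. Twenty patients are enrolled, and the procedure is called feasible if at least 15 succeed. Sections 2 and 12 state the same D90 threshold. None of the three names the dose that the percentage refers to.

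Section 9 sets the planning terms: "Prescribed dose is 14 Gy to the periphery of the GTV". Its next line reads "GTV coverage by the prescription dose will at least be 80"%, with D90 ≥ 80% in brackets. Section 4.1 also gives the prescription as 14 Gy in one fraction. Item 3.i of treatment planning in Section 9 provides that, where 14 Gy cannot be reached within the organ limits, the highest dose that respects those limits is delivered.

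Section 3.3 describes five earlier patients, with a "median GTV V90 of 77% (range 40-89%) and median GTV D90 of 75% (range 31-94"%). On dose it says "Median dose delivered was 14 Gy (range 12-18 Gy"), and on the cord, "In all cases the spinal cord/cauda maximum dose constraints were met". For the trial itself, Section 10 states: "Specific dosimetric parameters will include GTV V90, V100, V150, V200, D90", together with cord/cauda histograms.

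**The concern.** The D90 and V90 ranges in Section 3.3 contradict each other under the usual definitions. They are the only D90 results in the readable text, and Section 10 collects the same pair of measures in the trial. If the centre's own figures mix conventions, a reader may doubt which convention will be used to score the trial.

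The doubt matters because D90 carries the decision. Under item 3.i a compliant plan does not exceed the cord/cauda limit, so D90 is the half of the composite that can fail. The earlier doses ran from 12 to 18 Gy with no common prescription stated, and trial patients may also receive less than 14 Gy. For a patient given 12 Gy, 80% of that patient's own dose is 9.6 Gy, which is only 68.6% of 14 Gy: a pass on one reading and a failure on the other. Specific Aim 1 also seeks "to provide improved dosimetric coverage of lesions such that" the D90 threshold is met, which invites comparison with the earlier series.

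**Working it through.** **1. The plan's own table.** Inputs from Section 14: n = 20, cut-off 15. Formula: P(X ≥ 15) = Σ C(20, x) pˣ (1 − p)²⁰⁻ˣ for x = 15 to 20.

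| True rate | 55% | 60% | 65% | 70% | 75% | 80% | 85% | 90% |
|---|---|---|---|---|---|---|---|---|
| Printed | 0.055 | 0.126 | 0.245 | 0.416 | 0.617 | 0.804 | 0.933 | 0.989 |
| Recomputed | 0.0553 | 0.1256 | 0.2454 | 0.4164 | 0.6172 | 0.8042 | 0.9327 | 0.9887 |

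All eight agree. Nothing from Section 3.3 enters the calculation.

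**2. The conflict in Section 3.3.** D90 is the dose, as a percentage of the reference, that 90% of the volume receives or exceeds. V90 is the percentage of the volume receiving at least 90% of the reference. A cumulative dose-volume curve never rises, so D90 = 94% means that 90% of the volume receives at least 94%. Hence at least 90% of it receives at least 90%, and V90 ≥ 90%. The largest V90 printed is 89%. Rounding does not help: 93.5% is still above 90%, and anything below 89.5% is still below 90%. Swapping the labels fails too, since V90 = 94% would force D90 ≥ 90%, above 89%. The conflict is real if both ranges cover the same five patients against one reference dose.

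**3. Possible explanations.**
- V90 may be a slip for V100. A D90 of 94% is compatible with 89% of the volume receiving the full reference dose.
- The two measures may use different references A (for V90) and B (for D90). This needs 0.90 × A > 0.94 × B, so B < 0.957 × A. With D90 on 14 Gy, 94% is 13.16 Gy. With V90 on 18 Gy, the V90 level is 0.90 × 18 = 16.2 Gy, so there is no conflict.
- One figure may simply be wrong.

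None of these says how D90 will be computed for trial patients.

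**4. The reference dose for the trial.** Sections 4.1 and 9 give one prescription, 14 Gy. Section 9 places the D90 threshold beside the prescription dose. Item 3.i speaks of the dose delivered when the 14 Gy target cannot be met; it does not reset the prescription. Section 14 gives one rule without exceptions. Read together, the pass mark is 0.80 × 14 = 11.2 Gy for every patient.

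**5. Why the other reading would not serve the endpoint.** Suppose, for illustration, a plan on 14 Gy has D90 = 11.2 Gy (80%) and cord maximum 9.33 Gy. Scale the whole plan by 12/14. The cord maximum becomes 9.33 × 12/14 = 8.0 Gy and D90 becomes 9.6 Gy. Against 12 Gy, D90 is still 80%; against 14 Gy it is 68.6%. On the patient's own dose, scaling down never lowers the D90 percentage, so the requirement to meet coverage and cord limit together would lose its force. Only the fixed 14 Gy reference makes the composite a test, and it is the stricter reading.

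**6. Reduced-dose patients and the table.** Assume that m of 20 patients get less than 14 Gy and all fail against 14 Gy, while the others succeed with probability 0.80. The chance of declaring feasibility is then P(X ≥ 15) with n = 20 − m.

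| m | Overall success rate | P(declare feasible) | Printed neighbours |
|---|---|---|---|
| 0 | 80% | 0.804 | 0.804 at 80% |
| 1 | 0.80 × 19/20 = 76% | 0.673 | 0.617 at 75%, 0.804 at 80% |
| 2 | 0.80 × 18/20 = 72% | 0.501 | 0.416 at 70%, 0.617 at 75% |
| 3 | 0.80 × 17/20 = 68% | 0.310 | 0.245 at 65%, 0.416 at 70% |

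The drop is what the table already shows for a lower true rate. A patient who cannot be covered within the organ limits is a genuine feasibility failure and belongs in that rate. The documents do not give m.

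**7. The Section 9 phrase.** Coverage of 80% of the GTV by the prescription dose is V100 ≥ 80%. D90 ≥ 80% is V80 ≥ 90%. Neither implies the other: V100 = 80% with V80 = 85% meets only the first, and V100 = 60% with V80 = 92% meets only the second. Sections 2, 12 and 14, and the bracket in Section 9 itself, all state D90 ≥ 80%, so the endpoint is not in doubt.

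**The case for a change.** The strongest case does not rest on Section 3.3. Section 14 is silent on the reference dose, and the only sentence tying the threshold to the prescription describes a V100 measure, although Section 10 lists V100 and D90 separately. Item 3.i makes doses below 14 Gy foreseeable, and for those patients the choice of denominator can decide success or failure. With a cut-off of 15 of 20, one or two such patients could matter, and a choice left open could be made after the results are known. A single clause would close it at almost no cost.

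It stands that the text is loose and that the clause would be harmless. It does not stand that the endpoint is undetermined: choosing each patient's own dose would mean departing from the only prescription stated and from a rule written without exceptions. Section 10 collects D90 with the other dose-volume measures, so the scoring can be checked.

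The wish to compare with the earlier series carries little weight. Aim 1 sets fixed thresholds and Section 14 plans no comparison with those five patients, whose catheters were placed without this trial's navigation. Section 3.3 also does not say that the cord constraint they met was 8 Gy.

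**Conclusion.** No change to the plan follows. The V90 and D90 ranges in Section 3.3 cannot both be right on one reference dose, but that is a clerical matter in background data that feeds neither the 15-of-20 rule nor its table. The primary criterion reads as D90 of at least 11.2 Gy, 80% of the 14 Gy prescription, for every patient, including those given less under item 3.i. Analysts would supply that detail from Sections 4.1, 9 and 14. The Section 9 description of D90 as prescription-dose coverage is imprecise, but every statement of the endpoint uses D90.

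On this reading the decision rule and all eight table values are sound, and the documents show no effect on the feasibility verdict. The conclusion assumes the usual dose-volume definitions and that item 3.i alters the delivered dose without resetting the prescription. Two things could not be checked: how often the fallback will be used, and the representative plan in Appendix 3, whose figures are not in the available text.

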15.0 RESEARCH PARTICIPANT REGISTRATION AND RANDOMIZATION PROCEDURES

15.1 Research Participant Registration

Confirm eligibility as defined in the section entitled Criteria for Patient/Subject Eligibility.

Obtain informed consent, by following procedures defined in section entitled Informed Consent Procedures.

During the registration process registering individuals will be required to complete a protocol specific Eligibility Checklist.

All participants must be registered through the Protocol Participant Registration (PPR) Office at Memorial Sloan-Kettering Cancer Center. PPR is available Monday through Friday from 8:30am – 5:30pm at [contact]. Registrations must be submitted via the PPR Electronic Registration System(<http://ppr/>). The completed signature page of the written consent/RA or verbal script/RA, a completed Eligibility Checklist and other relevant documents must be

uploaded via the PPR Electronic Registration System.

16.0 DATA MANAGEMENT ISSUES

A Research Study Assistant (RSA) will be assigned to the study. The responsibilities of the RSA include protocol compliance, data collection, abstraction and entry, data reporting, regulatory monitoring, problem resolution and prioritization, and coordinate the activities of the protocol study team.

Research material from this study will be handled with the same confidentiality as patients' other medical data. The data collected for this study will be entered into a secure database. Source documentation will be available to support the computerized patient record.

16.1 Quality Assurance

Eligibility of patients will be verified with the principal investigator. Only the designated investigators will obtain informed consent. An assigned RSA will work with the principal investigators to ensure proper adherence to the protocol, eligibility verification, informed consent and data accuracy.

Routine data quality reports will be generated to assess missing data and inconsistencies. Accrual rates and accuracy of evaluations and follow-up will be monitored periodically throughout the study period and potential problems will be brought to the attention of the study team for discussion and action.

16.2 Data and Safety Monitoring

With the help of the RSA, the principal investigators will review each case at the time of enrollment to verify eligibility. The RSA will work with the principal investigators to ensure that the protocol is followed carefully.

The Data and Safety Monitoring (DSM) Plans at Memorial Sloan-Kettering Cancer Center were approved by the National Cancer Institute in September 2001. The plans address the new policies set forth by the NCI in the document entitled "Policy of the National Cancer Institute for Data and Safety Monitoring of Clinical Trials" which can be found at: <http://cancertrials.nci.nih.gov/researchers/dsm/index.html>. The DSM Plans at MSKCC were established and are monitored by the Office of Clinical Research. The MSKCC Data and Safety Monitoring Plans can be found on the MSKCC Intranet at: <http://mskweb2.mskcc.org/irb/index.htm>.

There are several different mechanisms by which clinical trials are monitored for data, safety and quality. There are institutional processes in place for quality assurance (e.g., protocol monitoring, compliance and data verification audits, therapeutic response, and staff education on clinical research QA and departmental procedures for quality control, plus there are two institutional committees that are responsible for monitoring the activities of our clinical trials programs. The committees: Data and Safety Monitoring Committee (DSMC) for Phase I and II clinical trials, and the Data and Safety Monitoring Board (DSMB) Institutional Review Board.

During the protocol development and review process, each protocol will be assessed for its level of risk and degree of monitoring required. Every type of protocol (e.g., NIH sponsored, in-house sponsored, industrial sponsored, NCI cooperative group, etc.) will be addressed and the monitoring procedures will be established at the time of protocol activation.

17.0 PROTECTION OF HUMAN SUBJECTS

There are no foreseen additional risks to the patients from this study. Every effort will be made to protect the rights of human subjects as per institutional policy. A full discussion of risk, benefits, expected toxicities/side effects, alternatives/options for treatment will be undertaken. No additional financial costs or burdens will result as a consequence of joining this study. Informed consent is a prerequisite to enrollment on the study.

In accordance with institutional policy, privacy and confidentiality of medical records will be strictly observed. All data pertaining to the study will also be likewise protected. The study is entirely voluntary. Patients who do not wish to participate in the study will be offered all treatment options including but not limited to those considered to be the standard of care.

17.1 Privacy

MSKCC's Privacy Office may allow the use and disclosure of protected health information pursuant to a completed and signed Research Authorization form. The use and disclosure of protected health information will be limited to the individuals described in the Research Authorization form. A Research Authorization form must be completed by the Principal Investigator and approved by the IRB and Privacy Board (IRB/PB).

17.2 Serious Adverse Event (SAE) Reporting

Any SAE must be reported to the IRB/PB as soon as possible but no later than 5 calendar days. The IRB/PB requires a Clinical Research Database (CRDB) SAE report be submitted electronically to the SAE Office at [contact]. The report should contain the following information:

Fields populated from CRDB:

- Subject's name (generate the report with only initials if it will be sent outside of MSKCC)
- Medical record number
- Disease/histology (if applicable)
- Protocol number and title

Data needing to be entered:

- The date the adverse event occurred
- The adverse event
- Relationship of the adverse event to the treatment (drug, device, or intervention)
- If the AE was expected
- The severity of the AE
- The intervention
- Detailed text that includes the following
 - A explanation of how the AE was handled
 - A description of the subject's condition
 - Indication if the subject remains on the study
 - If an amendment will need to be made to the protocol and/or consent form.

MEMORIAL SLOAN-KETTERING CANCER CENTER IRB PROTOCOL #: 12-260 A(4)

The PI's signature and the date it was signed are required on the completed report.

